One of the trial's safety endpoints is the incidence of acute inflammatory reactions (AIRs), defined as increase of pain by 30 mm on a 100 mm VAS and a self-reported synovial fluid effusion (i.e., joint swelling) within 3 days following i.a. injection. A similar definition based on a 30-mm increase in pain on VAS and observation of local swelling was used successfully in a trial in rheumatoid arthritis involving i.a. injections of interleukin-1 receptor antagonist (IL-1ra; anakinra (23)).

The extension phase of the trial will allow exploration of the drug's long-term safety.

Biomarker Assessment

Assessment of biomarkers of bone and joint tissue turnover is expected to identify candidate markers potentially predictive of response to treatment, prognostic for disease progression, or associated with response to the compound (see Section 7.6.1.).

Pharmacokinetic Assessment

The levels of sprifermin/FGF-18 in serum will be assessed 2 hours after the last dose of each cycle and will give an indication of whether sprifermin reaches the systemic circulation. Based on previous trials, systemic levels of sprifermin/FGF-18 are expected to be below the LLOQ.

Levels of sprifermin/FGF-18 in synovial fluid will be measured in order to give a first estimate of the residence time of sprifermin in the synovial fluid.

Evaluation of Health-related Quality of Life

The KOOS (see Section 7.7.1) is a knee-specific questionnaire designed to evaluate both short-term and long-term consequences of knee injury, including OA; it is intended for use in knee injury potentially leading to post-traumatic OA or in primary OA. The KOOS QOL subscale is more specific to QOL in subjects with knee OA than the more general MOS SF-36 (see below), and may better predict future need for knee replacement.

The MOS SF-36 (see Section 7.7.2) is a generic patient-reported health-related QOL instrument that is widely used in different diseases and conditions (including OA). MOS SF-36 results from this trial will be used to determine whether the MOS SF-36 is sensitive enough to measure changes in QOL in the trial population.

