7.4.1.3 Definition of the Adverse Event Reporting Period

The AE reporting period for safety surveillance begins when the subject is included into the trial (date of first signature of informed consent) and continues until the end of the trial's post-treatment extended follow-up phase, or until the subject's final trial visit in case of early withdrawal.

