Based on recent literature and other trial experience (45, 46), the subject discontinuation rate is estimated to be close to 30% at two years. Assuming a 30% drop-out rate, a total of 545 subjects should be randomized (109 subjects per group) in order to detect an overall treatment effect.

In order to be able to demonstrate that structure improvement translates into symptomatic benefit, it is important that the study be adequately powered to detect significant differences in normalized WOMAC scores. With 76 evaluable subjects per treatment group, the power to show a statistically significant difference between at least one active treatment group and the placebo group for the secondary WOMAC endpoints ranges from 69% to 87% for the total score, from 80% to 99% for the pain score and from 53% to 83% for the function score, depending on the expected mean difference from placebo (see Table 3).

Table 3 Power Calculations for Pairwise Differences (Sprifermin versus Placebo) on Normalized WOMAC Scores with 76 Evaluable Subjects per Treatment Group

	Expected mean difference from Placebo	Common SD	Power
Total Score - Normalized (range 0-100 points)	8 points	20	69%
	9 points		79%
	10 points		87%
Pain Score - Normalized (range 0-100 points)	10 points	22	80%
	15 points		99%
Function Score - Normalized (range 0-100 points)	7 points	21	53%
	9 points		75%
	10 points		83%

SD: standard deviation; WOMAC: Western Ontario and McMaster Universities Osteoarthritis Index

For reference, a difference of 10 points from placebo in the normalized WOMAC scores is considered as clinically meaningful (highlighted in bold type in the table).

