Additionally subjects identified in the Note To File: "NTF_QC of primary endpoint MRI_FORWARD_17MAY2016", will be excluded from the PP.

"Based on input from the IDMC (ad hoc meeting, 21 June 2016), subjects will be excluded from the Per Protocol analysis if they have significant pre-treatment MRI lesions that would interfere with analysis of the primary endpoint. Accordingly, the following 2 subjects will be excluded from Per Protocol analysis, although retained in ITT, mITT, and Safety analyses:

Second Intention-to-Treat Analysis Set

The Second ITT (ITT2) Analysis Set will include all subjects from the ITT Analysis Set who have at least one valid MRI assessment or one X-ray measurement available or one WOMAC measurement available after day 819 (i.e., during the 3-year Extended Follow-up Phase [Week 104, Year 2] and up to day 1849 [Week 260, Year 5]).

Safety Analysis Set

The Safety Analysis Set will include all subjects who receive at least one dose of trial treatment. Subjects will be analyzed according to the actual treatment they receive. In case of deviations from planned treatment, after un-blinding placebo patients receiving at least one active injection, will conservatively be allocated to the lowest of the possible planned Sprifermin dose groups. Please refer to the "Analysis Sets" document for more details.

Pharmacokinetic Analysis Set

The PK Analysis Set will include all subjects from the Safety Analysis Set who have at least one available serum or synovial fluid measurement.

PGX Analysis Set

The PGX Analysis Set will include subpopulation of subjects from the ITT Analysis Set with informed consent allowing for analyses of genetic data, and who have PGX measurement needed for the analysis specified in Section 16.4.

Tables and figures will be presented on separate analysis set as presented in Table 2 below:

Table 2 Overview of analyses by Analysis Set

	DBPC Treatment Phase			Follow-up Phase	Both phase	
Analyses	Intent-to- Treat Analysis Set (ITT)	Modified ITT (mITT)	Per Protocol Analysis Set (PP)	PGX Analysis Set (PGX)	Second ITT (ITT2)***	Safety Analysis Set (Safety)
Demography and Baseline Assessments (incl. other baseline characteristics section 13.3)	✓	✓	✓	✓	√	√
Concomitant Therapies	✓	✓	✓		✓	✓
Compliance and Exposure	✓	✓	✓	✓		✓
MRI Efficacy: Primary and secondary		√	✓		√	
Efficacy: Secondary (non MRI) with and without LOCF	✓		√ *		✓	
Exploratory endpoints – additional analyses end of section 16.5	/**				√ **	

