Summary statistics will be presented per treatment group and where relevant for 'all subjects'. Summary statistics will be presented also per country. The summary statistics presented for quantitative variables will be the number of observations (n), the number of missing values (missing), mean, standard deviation (SD), median, first and third quartiles (Q1, Q3), and minimum (min) and maximum (max) values. The mean, SD, median, first and third quartiles values will be presented with one more decimal places as the raw data. The minimum and maximum values will be reported to the same number of decimal places as the raw data. In general, the maximum number of decimal places reported shall be four for any summary statistic.

The summary statistics presented for categorical data will be the number of observations (n), the number of missing values (missing), and the count and percentage of subjects in each category at the relevant time point(s). Percentage will be given with one decimal place.

The summary statistics presented for adverse events will be number of observations (n), the percentage of subjects (%), overall and per system organ class (SOC) and PT.

Apart from the trend test for AIRs, all confidence intervals (CI) and statistical tests will be twosided. Calculation of differences between treatment groups of continuous endpoints and corresponding CIs, will be normal based using unequal variances. CIs will be presented with one more decimal place than the raw data. P-values greater than or equal to 0.001, in general, will be presented with three decimal places. However, if a p-value is only presented with four decimal places (by SAS) it will not be rounded further, but will be presented with four decimal places. P-values less than 0.001 will be presented as "<0.001", while P-values greater than 0.999 will be presented as ">0.999".

Plots showing mean absolute change from baseline to each time point in key endpoints (structure and WOMAC) within each treatment group will be provided for the ITT analysis set for non-MRI endpoints, and for the mITT analysis set for MRI endpoints.

Age, sex and race will be reported on all by-subject listings unless otherwise specified. Sex will be abbreviated as: female (F) and male (M). Race will be abbreviated as: American Indian or Alaska Native (AI), Asian (AS), Black or African American (BL), Native Hawaiian or other Pacific Islander (NH), White (WH) and Other (O).

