17.1 Adverse Events

Adverse Events will be coded using latest version of MedDRA at the end of each of 2 reporting periods (2 year and 5 year analyses).

For 2 years analysis: Treatment-emergent adverse events (TEAEs) are defined as those adverse events that either start or worsen in severity on or after the date of first dose of study treatment (first injection) until 30 days from last dose of study treatment (last injection). Where dates are missing or partially missing, adverse events will be assumed to be treatment-emergent, unless there is clear evidence (through comparison of partial dates) to suggest that the adverse event started prior to the first dose of study treatment or after the subject's last treatment (+30 days). See appendix 20.4 for details.

For 5 years analysis: All AEs from the complete duration of the study will be summarized (but not TEAEs, as these are not relevant per definition above). There will be no summaries of TEAEs for the 5 years analysis only AE

Pre-treatment emergent adverse events, i.e. adverse events starting between date of informed consent and until date of first dose of study treatment will be tabulated separately.

Adverse events of special interest (AESI) will include the following:

Injection site reactions will be summarized by treatment group and PT. These will be identified using higher level term (HLT) "Injection site reactions".

Similarly, musculoskeletal complaints (eg. Back pain, neck pain), will be identified using prespecified SOC "Musculoskeletal and connective tissue disorders" and will be summarized by treatment group and by PT.

In addition, Neoplasms will be identified using pre-specified SOC "Neoplasms benign, malignant and unspecified (including cysts and polyps)" and will be summarized by treatment group and by PT.

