17.1.1 All Adverse Events

AEs will be summarized as follows:

- Overview of all AEs
- TEAE by SOC and PT
- TEAE by severity
- TEAE by relationship
- Local TEAE by SOC and PT
- Local TEAE by severity
- Local TEAE by relationship
- Systemic TEAE by SOC and PT
- Systemic TEAE by severity
- Systemic TEAE by relationship
- Any serious adverse events (SAEs) further specified in Section 17.2.2
- Any non-serious AEs (at least 5% in any treatment group) by SOC and PT
- Most frequent TEAEs (at least 5% in any treatment group) by PT only
- Treatment emergent Injection Site Reactions by PT only (as described in Section 17.1)
- Treatment emergent Musculoskeletal disorders by PT only
- Treatment emergent Neoplasms by PT only

All AE and TEAE summaries will report the number and percentage of subjects, overall and by SOC and PT. AESI will be summarized by subjects (and %).

Each summary will be ordered alphabetically for SOC, and decreasing frequency for PT within SOC overall.

Subjects can contribute to more than one relationship or severity count per SOC/PT. In this case, the strongest relationship or worst severity will be used. If severity or relationship is missing, the worst case will be assumed.

Clinical trial.gov and EudraCT requirements: Summary table for non-serious AEs by SOC and PT (excluding SAE) with at least 5% in any treatment group will be provided.

A by-subject listing of all adverse events (including non-treatment-emergent events) will be provided. This listing will be presented by treatment group and will include: country, subject identifier, age, sex, race, target knee (left/right), adverse event (SOC, PT, and verbatim term), date of onset, date of resolution, duration, severity, seriousness, action taken, outcome and causal relationship to treatment.

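### The Year-3 and 5-year adverse event summaries give only percentages of dosed subjects, so risks of events that accrue over time are understated when subjects leave early

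*SAP*

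**What the plan says.** Protocol 5.2 gives long-term safety as one purpose of the follow-up: "The extension phase of the trial will allow exploration of the drug's long-term safety". SAP 17.1 makes neoplasms one of three groups of adverse events of special interest (AESI).

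For the 5-year analysis, SAP 17.1 says: "All AEs from the complete duration of the study will be summarized (but not TEAEs, as these are not relevant per definition above"). That sentence sets which events are counted, not how. The measure comes from two other places:

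- SAP 17.1.1: "All AE and TEAE summaries will report the number and percentage of subjects, overall and by SOC and PT". It reports the AESI in the same way.
- SAP Section 11: "The summary statistics presented for adverse events will be number of observations (n), the percentage of subjects".

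SAP Section 8 adds a Year-3 analysis that repeats the Year-2 safety analysis.

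The denominator is set in SAP Section 10: "The Safety Analysis Set will include all subjects who receive at least one dose of trial treatment". Length of observation plays no part in it. Under Protocol 7.4.1.3, AE reporting runs to the end of the extended follow-up, "or until the subject's final trial visit in case of early withdrawal". Protocol 8.1 plans for substantial loss: "Assuming a 30% drop-out rate, a total of 545 subjects should be randomized".

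Neither document plans person-years of observation, person-year event rates, or a time-to-event summary for AEs. Exposure in SAP Section 15 runs from first to last injection, which is not observation time.

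**The concern.** A percentage of all dosed subjects treats everyone as if observed for the full 5 years. Events after a subject leaves are not captured, but the subject stays in the denominator. This matters little for reactions within days of an injection. For events that build up over years, such as neoplasms and many SAEs, the percentage falls as dropout rises, whatever the drug does.

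Two things are at stake. The absolute 5-year risk would be reported too low in every arm. And if one arm were followed for less time than another, its percentage would be lower for that reason alone, which could hide an excess or create an apparent one.

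**Working it through.** **Plan's own figure.** The dropout allowance reproduces: 76 / (1 − 0.30) = 108.6, rounded up to 109 per group, and 5 × 109 = 545. The 30% is therefore the plan's own two-year loss.

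**Inputs**

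- Two-year dropout d = 30% (Protocol 8.1).
- Follow-up of 5 years (2 treatment, 3 extended).
- Assumed, not in the documents: event hazard h = 0.01 per year, constant; dropout independent of events.
- Dropout in years 2 to 5 is not stated. The range runs from none to the same yearly hazard as in years 0 to 2.

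**Follow-up**

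- Dropout hazard r = −ln(0.70)/2 = 0.178 per year.
- Same hazard to year 5: 0.70^2.5 = 41% retained; mean follow-up (1 − e^(−5r))/r = 3.31 years.
- No loss after year 2: mean follow-up 0.30/r + 3 × 0.70 = 3.78 years.

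**Understatement in a single arm**

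- True 5-year risk: 1 − e^(−0.05) = 4.88%.
- Crude, same hazard to year 5: h/(h+r) × (1 − e^(−5(h+r))) = 0.0531 × 0.610 = 3.24%, or 66% of the true risk.
- Crude, no loss after year 2: h/(h+r) × (1 − e^(−2(h+r))) + e^(−2(h+r)) × (1 − e^(−3h)) = 1.67% + 2.03% = 3.69% before rounding the terms, or 76% of the true risk.
- In between: 10% or 20% further loss over years 2 to 5 gives 3.59% or 3.49%.
- At hazards of 0.005 and 0.02 the fraction captured is almost unchanged (66% to 76% and 67% to 76%).
- Events that can occur only in years 2 to 5: true risk 1 − e^(−0.03) = 2.96%; crude 1.60% to 2.07%, or 54% to 70%.

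**Between arms.** The documents give no dropout by arm, so these are scenarios. The true hazard is 0.01 in both arms. The first crude figure or ratio is for the same dropout hazard to year 5, the second for no loss after year 2.

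| Two-year dropout, placebo / active | Crude %, placebo | Crude %, active | Crude ratio | Person-year rate ratio |
|---|---|---|---|---|
| 30% / 30% | 3.24, 3.69 | 3.24, 3.69 | 1.00, 1.00 | 1.00 |
| 25% / 35% | 3.49, 3.89 | 3.00, 3.49 | 0.86, 0.90 | 1.00 |
| 20% / 40% | 3.75, 4.09 | 2.77, 3.29 | 0.74, 0.80 | 1.00 |
| 40% / 20% | 2.77, 3.29 | 3.75, 4.09 | 1.35, 1.24 | 1.00 |

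**Where a person-year rate would do harm.** Suppose local events arise only while injections continue (to Week 80), with equal hazards in both arms. The crude ratio is then 0.95 (25% / 35%) or 0.90 (20% / 40%). A rate divides by person-years to the final visit, so its ratio is the crude ratio times placebo over active mean follow-up:

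- 25% / 35%: 0.949 × 3.57/3.06 = about 1.10; with no later loss, 0.949 × 3.99/3.57 = 1.06.
- 20% / 40%: 0.900 × 3.83/2.82 = 1.22; with no later loss, 0.900 × 4.19/3.37 = 1.12.

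For such events the rate shows an excess that does not exist, and in most of these scenarios it is further from 1 than the crude ratio.

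**Size against chance.** With 109 per arm and h = 0.01, expected counts are 109 × 3.24% = 3.5 to 109 × 4.88% = 5.3 per arm. For 3.8 against 3.3 events, the 95% interval for a ratio extends by a factor of about e^(1.96 × √(1/3.8 + 1/3.3)) = 4.4 either way.

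**The case against.** The case on the other side has real force:

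- **The percentage is an observed proportion.** The SAP does not call it a 5-year risk, and follow-up reporting is descriptive. That is true, but a rate is descriptive too, and readers will take a 5-year percentage as a risk.
- **Follow-up can be judged from other outputs.** SAP Section 12 plans disposition by arm and time to study termination, and SAP 17.1.1 a by-subject listing with onset dates. These supply the ingredients, but no follow-up-adjusted incidence.
- **The 30% may overstate lost observation.** It sizes the two-year MRI endpoint, and Protocol 7.1.5 lets subjects who stop treatment continue in follow-up. This stands; nothing in the documents fixes the loss after year 2.
- **Chance will often exceed the bias**, given 3 to 5 expected events per arm. This also stands. Nor do person-year rates cure informative dropout.
- **The table shells are not visible.** SAP Section 19 makes them part of the plan, so further outputs may exist there.

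Two stronger readings are tempting. A reader might infer that arm comparisons are biased, for example because injection burden drives dropout in the active arms. The documents do not support this: all arms have the same injection schedule, placebo included, and no dropout by arm is given. A reader might also infer that late neoplasms go unreported. SAP 17.1.1 lists only treatment-emergent neoplasms, and treatment-emergent summaries are dropped at 5 years, so a separate 5-year neoplasm table is uncertain. But neoplasms remain within the summary of all AEs.

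**Conclusion.** The point holds as a descriptive weakness. Under the planned 30% two-year loss and a constant event hazard, the crude percentage captures about 66% to 76% of the true 5-year risk for events that accrue over time. The low end assumes that the dropout hazard continues to year 5, the high end that nobody leaves after year 2. With equal dropout across arms the between-arm ratio is essentially unaffected. Distortion of arm comparisons is conditional on unequal follow-up, which the documents neither state nor rule out. No test, alpha level or decision rule in the plan depends on this. The change is worth making because long-term safety is a stated purpose of the follow-up and the plan itself singles out neoplasms.

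**What to change.** In SAP 17.1 and 17.1.1, for the Year-3 and 5-year analyses:

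1. Keep the crude percentages and print total person-years of observation per arm beside them.
2. For neoplasms (all onsets, not only treatment-emergent) and SAEs, add first events per 100 person-years from first injection to event, final visit or data cut, with the difference from placebo and its 95% CI.
3. For the same two groups, add a cumulative-incidence curve by arm.
4. Do not apply 5-year person-year rates to local AEs or injection-site reactions. Keep those per injection or cycle, or within the dosing window.

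The cost is SAP wording and a few outputs. The dates of first injection, AE onset and study termination are already collected, and no visit, dose or clinical rule changes. The rates assume roughly constant hazards, which the curves check; intervals will be wide.

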17.1.1 All Adverse Events

AEs will be summarized as follows:

- Overview of all AEs
- TEAE by SOC and PT
- TEAE by severity
- TEAE by relationship
- Local TEAE by SOC and PT
- Local TEAE by severity
- Local TEAE by relationship
- Systemic TEAE by SOC and PT
- Systemic TEAE by severity
- Systemic TEAE by relationship
- Any serious adverse events (SAEs) further specified in Section 17.2.2
- Any non-serious AEs (at least 5% in any treatment group) by SOC and PT
- Most frequent TEAEs (at least 5% in any treatment group) by PT only
- Treatment emergent Injection Site Reactions by PT only (as described in Section 17.1)
- Treatment emergent Musculoskeletal disorders by PT only
- Treatment emergent Neoplasms by PT only

All AE and TEAE summaries will report the number and percentage of subjects, overall and by SOC and PT. AESI will be summarized by subjects (and %).

Each summary will be ordered alphabetically for SOC, and decreasing frequency for PT within SOC overall.

Subjects can contribute to more than one relationship or severity count per SOC/PT. In this case, the strongest relationship or worst severity will be used. If severity or relationship is missing, the worst case will be assumed.

Clinical trial.gov and EudraCT requirements: Summary table for non-serious AEs by SOC and PT (excluding SAE) with at least 5% in any treatment group will be provided.

A by-subject listing of all adverse events (including non-treatment-emergent events) will be provided. This listing will be presented by treatment group and will include: country, subject identifier, age, sex, race, target knee (left/right), adverse event (SOC, PT, and verbatim term), date of onset, date of resolution, duration, severity, seriousness, action taken, outcome and causal relationship to treatment.

17.1.2 Adverse Events Leading to Discontinuation

The following summaries will be presented

- TEAE leading to discontinuation
- Local TEAE leading to discontinuation
- Systemic TEAE leading to discontinuation

A by-subject listing of TEAEs leading to discontinuation will be provided.

The time to discontinuation due to an AE in days will be calculated as follows:

Date of discontinuation due to an AE – Date of first injection + 1

There are two types of discontinuations caused by an AE, the criteria are: action = drug withdrawn OR other action = led to study termination. These are summarized collectively as discontinuations due to AE. The date of discontinuation is the first date where any of the two types of discontinuations occurs.

17.2 Deaths, Other Serious Adverse Events, and Other Significant Adverse Events

17.2.1 **Deaths**

All AEs leading to death will be listed.

